## **Amendments**

Amendment 1: 10/1/2021

Summary of Changes:

1. The primary outcome was changed to opioid consumption in the first 24 hours and 24-48 hours after surgery.
2. The secondary outcomes are now abdominal wall sensation with ice and pinprick, pain scores 72 hours after surgery, and opioid consumption 48-72 hours after surgery.
3. Sample Size Considerations was updated to reflect the changes in the study outcomes.

## Specific Aims

Pain management after major abdominal surgery remains challenging. The best-accepted traditional analgesic approach is continuous epidural analgesia. However, epidural analgesia is rapidly being replaced by transversus abdominis plane (TAP) blocks. TAP infiltration is an alternative to epidural blocks for providing postoperative analgesia to the anterior abdominal wall. TAP infiltrations are relatively easy to perform, generally safe, and can be performed in patients who are anti-coagulated. TAP infiltration can be performed as a single injection, or a catheter can be inserted for continuous local anesthetic infusion.

Single shot plain bupivacaine is often used for TAP blocks, but plain bupivacaine provides <24 hours of analgesia. Catheters provide analgesia for longer, but they are difficult to position properly and difficult to maintain in the proper anatomical location. An alternative to TAP catheters is infiltration of liposomal bupivacaine which, in other sites, lasts up to three days. But whether liposomal bupivacaine is preferable to plain bupivacaine for TAP blocks remains controversial, with available studies being sparse and inconclusive.

We therefore proposed to compare single-shot TAP infiltration with liposomal bupivacaine, plain bupivacaine, and placebo on length of anesthetic effect determined by the opioid consumption. We will evaluate the following specific aims, all of which will be assessed over 72 hours, or the duration of hospitalization if shorter:

**Primary Aim 1:** To assess the relative effects of TAP blocks with liposomal bupivacaine, plain bupivacaine and placebo on cumulative opioid consumption in first 24 hours with TAP blocks.

**Primary Aim 2:** To assess the relative effects of TAP blocks with liposomal bupivacaine, plain bupivacaine and placebo on cumulative opioid consumption in 24 to 48 hours with TAP blocks.

**Secondary Aim 1:** To assess the relative effects of TAP blocks with liposomal bupivacaine, plain bupivacaine and placebo on the duration of abdominal wall analgesia (determined by pinprick and cold).

**Secondary Aim 2:** To assess the relative effects of TAP blocks with liposomal bupivacaine, plain bupivacaine and placebo on pain after surgery in first 72 hours.

**Secondary Aim 3:** To assess the relative effects of TAP blocks with liposomal bupivacaine, plain bupivacaine and placebo on cumulative opioid consumption 48 to 72 hours.

**Tertiary Aim 1:** To compare the effects of TAP blocks with liposomal bupivacaine, plain bupivacaine, and placebo on a composite of postoperative opioid-related side effects.

**Tertiary Aim 2:** To compare the effects of TAP blocks with liposomal bupivacaine, plain bupivacaine and placebo on patients' satisfaction with their pain treatments after 72 hours/discharge surgery.

**Tertiary Aim 3:** To assess total and specific costs of hospital care in patients receiving TAP with liposomal bupivacaine vs. those with plain bupivacaine following abdominal surgery. [2 groups only]

**Tertiary Aim 4:** To compare the effects of TAP blocks with liposomal bupivacaine, plain bupivacaine and placebo on patients' pain with movement for 72 hours/discharge surgery.

**Tertiary Aim 5.** To compare the effects of TAP blocks with liposomal bupivacaine, plain bupivacaine and placebo on patients' mobility for 72 hours/discharge surgery.

## 1. Background

### A. Postoperative Pain

Pain is a psychological sensory experience that is provoked by surgical tissue injury. Postoperative pain results from a combination of nociceptive and inflammatory components. The nociceptive component results from activation of peripheral sensory neurons damaged by surgical incision and fades gradually as tissues heal. The inflammatory component enhances pain sensitivity via release of mediators from surgically injured tissue. Central neuronal sensitization also seems to contribute to postoperative pain and hyperalgesia. Both mechanisms contribute to resting pain in and around surgical incisions. Movement of wounds or touching them, breathing, coughing, and gastrointestinal motility can all provoke pain.

Postoperative pain causes a number physiological and psychological consequence, which potentially worsen outcomes. For example, inadequate perioperative analgesia is associated with myocardial ischemia, impaired wound healing, delayed gastrointestinal motility, atelectasis, and postoperative pneumonia. Furthermore, poorly controlled acute pain is strongly associated with development of persistent incisional pain, which can be devastating for patients.

### B. Postoperative pain management and Regional Analgesia

Pain management after major abdominal surgery is difficult and complicated. Thirty percent of patients report severe postoperative pain and 47% report moderate pain. Furthermore, 10-40% report persistent pain after abdominal and pelvic surgery. Multimodal analgesia combines various classes of drugs in an effort to provide good analgesia with few side effects. But the most common approaches are a combination of an opioid and non-opioid, with or without regional anesthesia-analgesia. Opioids cause various complications including ileus, sedation, and hyperalgesia. Opioids also impair cellular and humoral immune function in humans, thereby potentially enhancing infection risk. But the most lethal complication of opioid use is respiratory depression which has been identified as a safety target by the Joint Commission on Hospital Accreditation. Reducing perioperative opioid use is thus a clinical priority.

Regional Anesthesia or analgesia reduces the need for high-dose opioids. Regional analgesia techniques can be categorized as neuraxial (spinal and epidural blocks) that involve injection of local anesthetics around the spinal cord, or as peripheral nerve blocks that involve local anesthetic administration near peripheral nerves. The basis of regional analgesia is local anesthetics which locally block voltage-gated sodium channels, thus interrupting nerve conductions and causing regions to be insensitive to pain. Peripheral nerve blocks, especially, have become popular in recent decades largely because improvements in ultrasound technology make blocks faster and safer — and more importantly, because peripheral nerve blocks speed recovery and improve patient satisfaction.

[figure not shown]
Surgery provokes a stress response which releases catecholamines, cortisol, and inflammatory cytokines systemically. The stress response is associated with increased catabolism, immunosuppression, poor postoperative outcomes, and prolonged recovery. Regional anesthesia blocks afferent neural transmission from reaching the central nervous system and activating the stress response, thereby blocking descending efferent activation of the sympathetic nervous system. In clinical practice, regional anesthesia has proven to be superior to systemic opioids alone after thoracic, abdominal, gynecological, and orthopedic surgeries. Studies have consistently shown that regional anesthesia reduces postoperative pulmonary, gastrointestinal, and cardiac morbidities. Furthermore, there is evidence that RA decreases postoperative morbidity and mortality, and shortens postoperative hospitalization.

Epidural analgesia is the reference method for controlling post-operative pain after abdominal surgery. However epidural analgesia provokes hypotension, delays mobilization and discharge. Furthermore, catheter related problems are common, as is failure of epidural analgesia. Rarely, epidural analgesia results in inadvertent dural puncture, epidural hematoma, abscess, cord compression, and permanent paraplegia due to hematoma. An important limitation of epidural analgesia is that it should not be used in anticoagulated patients. These limitations have prompted clinicians to use alternative blocks, including the transversus abdominal block.

### **C. Transversus Abdominis Block**

Transversus Abdominis Block was described by Rafi in 2001 and provides post-operative analgesia for anterior abdominal wall. The target area of the local anesthetics is between the transvers abdominis and internal oblique muscle to block the spinal nerves (T6-L1). There are various types of TAP blocks, including intercostal/subcostal, lateral/classical, anterior, and posterior approaches.

**Figure 1: 4-quadrant TAP block**

Ultrasound-guided TAP blocks are easier and safer than epidural blocks, and complications are rare. TAP blocks are generally performed with a single injection, because catheters are tricky to insert properly and are frequently dislodged, especially when they are near the surgical site. TAP blocks have been used for various types of

surgeries including open appendectomies, hysterectomies, caesarean deliveries, abdominoplasties, prostatectomies, renal transplantation, and laparoscopic procedures. In open gynecologic surgeries, cesarean deliveries, and open gastrectomies, bilateral TAP blocks provides better analgesia than placebo groups.

All anterior branches of spinal nerves communicates, each segmental nerve supplies different areas and therefore analgesic effect and sensorial distribution of local anesthetics vary. Four-quadrant TAP blocks (Bilateral Dual) were described by Borglum et al. and provides wider coverage for upper- and lower-abdominal wall incisions because there is no communication between upper and lateral TAP spaces. (Figure 1). Dual blocks combine subcostal and lateral/posterior TAP blocks, thus providing complete coverage. Four quadrant TAP blocks should be performed to have good coverage especially for any incision that goes above umbilicus.

TAP blocks only provide somatic pain relief; they therefore provide analgesia for surgical incisions, but not for visceral pain. Numerous studies show that TAP block with plain bupivacaine provided substantially better analgesia and reduced opioid consumption compared to unblocked or placebo patients for up to 24 hours. TAP blocks with conventional local anesthetics including bupivacaine, ropivacaine and levobupivacaine in TAP block provide safe and effective analgesia, but only for the initial 24 postoperative hours. Long-acting local anesthetics are an alternative that might provide analgesia through the initial and most painful postoperative days.

#### **D. Liposomal bupivacaine (Exparel; bupivacaine liposome injectable suspension, Pacira Pharmaceuticals, Inc., Parsippany, NJ USA)**

Exparel is the prolonged-release formulation of the bupivacaine used for a single-shot infiltration of surgical sites or for nerve blocks. Exparel was approved by the US Food and Drug Administration (FDA) in 2011 for infiltration blocks, and in 2018 it received approval for the interscalene brachial plexus block.

Liposomal bupivacaine depofoam technology is based on multiple microscopic spherical particles with many aqueous chambers separated by lipid membranes. When refrigerated, the particles are stable; but after injection of liposomal bupivacaine into soft

tissue, bupivacaine is released from the multivesicular liposomes. The components of depofoam particles are non-toxic and clinical trials have demonstrated no adverse events. Furthermore, this technology previously has been safely used in various settings and provides sustained release of bupivacaine in other target areas. Liposomal bupivacaine administration produces dose-dependent increases in plasma bupivacaine concentrations, and that the half-life of liposomal bupivacaine was almost twice that of plain bupivacaine. However, maximum plasma concentrations are no higher with plain than liposomal bupivacaine.

a. Infiltration and liposomal bupivacaine

Postsurgical pain is intense in first few days and liposomal bupivacaine may be good option for controlling post-surgical pain. Many studies have evaluated infiltration of liposomal bupivacaine. Golf et al, for example, compared liposomal bupivacaine and placebo in bunionectomies. Cumulative pain scores were lower, and the time to first opioid use was significantly prolonged by liposomal bupivacaine. Hass et al. compared bupivacaine and various doses of liposomal bupivacaine in hemorrhoidectomies and found progressive reductions in opioid consumption as the dose of liposomal bupivacaine increased. Postoperative opioid consumption was significantly lower in patients given 266 mg of Exparel than in those given plain bupivacaine over 12 to 72 hours postoperatively. Local infiltration of liposomal bupivacaine also reduced postoperative pain compare with plain bupivacaine. A recent meta-analysis of 10 randomized wound infiltration studies concluded that cumulative pain scores were improved with liposomal bupivacaine through 24-72 hours. First use of opioid rescue medication was also delayed, and patient were more satisfied and experienced fewer opioid-related side effects.

A systematic review that evaluated liposomal bupivacaine infiltration for total hip arthroplasty showed that local liposomal bupivacaine infiltration reduced pain score, nausea and vomiting, and opioid consumption. However, this analysis was weakened by inclusion of studies with small sample sizes and others that were observational. The PILLAR cohort study compared liposomal and plain bupivacaine infiltration for total knee arthroplasty and showed that 10% of patients in liposomal bupivacaine group were opioid free. Total opioid consumption and pain intensity score also less when compared to

bupivacaine group. These PILLAR study results suggest that local infiltration of liposomal bupivacaine is analgesic and reduces or even eliminates the need for opioids after total knee arthroplasty. A number of studies report that liposomal bupivacaine has good efficacy and safety profiles in patients having knee, hip, and shoulder replacements. Liposomal bupivacaine has also been effective in plastic surgical procedures including mammoplasty and abdominoplasty, and provides longer pain relief. However, dose heterogeneity and small sample sizes make these results difficult to interpret.

b. Nerve block and liposomal bupivacaine

Single-shot peripheral nerve blocks with liposomal bupivacaine have distinct advantages compared to a continuous catheter. Specifically, patients given liposomal bupivacaine will not require infusion pumps and cannot develop catheter-related infection, hematoma, or dislodgement. Because liposomal bupivacaine was only recently approved for peripheral nerve blocks, and only at one site, there is currently little information about the approach. However, Hadzic et al. compared liposomal bupivacaine to placebo for femoral nerve blocks and found lower pain score and decreased opioid consumption were reduced. A retrospective analysis of peripheral nerve blocks with liposomal bupivacaine suggests that safety and the side effect profile are similar with bupivacaine and placebo.

Intercostal nerve blocks with liposomal bupivacaine were evaluated after thoracic surgeries and compared with plain bupivacaine. Liposomal bupivacaine reduced hospital duration — but curiously without a reduction in postoperative pain score or opioid use. Further studies are clearly needed to evaluate the efficacy of liposomal bupivacaine in nerve blocks.

c. TAP block and liposomal bupivacaine

So far only a few trials directly compare liposomal and plain bupivacaine for TAP blocks, and there is no consensus among them. According to a Cochrane systemic review, evidence is lacking for the efficacy of liposomal bupivacaine in TAP blocks, and concludes that there is no advantage to use of liposomal bupivacaine for this indication. It is important to recognize, though, that this conclusion is based on lack of evidence for benefit rather than robust evidence against. In another study, Guarre et al. compared

plain and liposomal bupivacaine in TAP blocks for laparoscopic colorectal surgery. Patients treated with liposomal bupivacaine required less opioid, had earlier return of bowel function, and left the hospital sooner. Hutchins et al. showed that TAP blocks with liposomal bupivacaine provided long-lasting analgesia compared to plain bupivacaine for laparoscopic-assisted donor nephrectomy, and reduced nausea and vomiting and the duration of hospitalization. In contrast, Ha et al. compared liposomal bupivacaine and plain bupivacaine in TAP blocks for breast reconstruction and reported no benefit.

### **E. Rationale of the Study**

The recent enhancement of conventional bupivacaine with encapsulated bupivacaine much prolongs the duration-of-action and resulting pain control with a single application. TAP blocks appear to be easier to perform (especially with ultrasound guidance), safer, relatively inexpensive, and can be used safely in patients who are anti-coagulated. However, the literature is scarce on comparison of plain bupivacaine versus liposomal bupivacaine in TAP blocks. Some clinicians therefore question the efficacy and benefit of liposomal bupivacaine for TAP blocks, especially considering the cost of liposomal bupivacaine. We therefore aim to compare the analgesic efficacy of TAP blocks with liposomal bupivacaine, plain bupivacaine, and placebo in patients who are scheduled for major abdominal surgery.

## **2. Study Objectives**

We will prospectively compare the analgesic efficacy of TAP blocks with liposomal bupivacaine, plain bupivacaine, and placebo in patients who are scheduled for major abdominal surgery. The proposed research will have the following aims:

### ***Primary Aims***

#### ***Primary Aim 1:***

To assess the relative effects of TAP blocks with liposomal bupivacaine, plain bupivacaine and placebo on opioid consumption in first 24 hours post surgery.

***Hypothesis.*** Opioid consumption over the initial 24 hours after major abdominal surgery is less when four-quadrant TAP blocks are performed with liposomal bupivacaine and plain bupivacaine compared to placebo. Opioid consumption will be evaluated as morphine sulfate equivalents; a difference of at least 10 mg in first 24 hours will be considered to be a clinically meaningful difference.

#### ***Primary Aim 2:***

To assess the relative effects of TAP blocks with liposomal bupivacaine, plain bupivacaine and placebo on opioid consumption between 24 and 48 hours post surgery.

***Hypothesis.*** Opioid consumption between 24 and 48 hours after major abdominal surgery is less when four-quadrant TAP blocks are performed with liposomal bupivacaine than with plain bupivacaine or placebo. Opioid consumption will be evaluated as morphine sulfate equivalents; a difference of at least 10 mg will be considered to be a clinically meaningful difference.

Criteria for success will be 1) superiority of bupivacaine and exparel groups over placebo and noninferiority between plain bupivacaine and exparel groups in the first 24 hours of opioid consumption and superiority of exparel group over placebo and bupivacaine in the 24-48 hours opioid consumption.

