#### ***Criterion for success of each intervention in each period.***

0-24 hours: for each of bupivacaine and exparel, success will be concluded if found to be superior over placebo (i.e., less opioid consumption). As well, exparel or bupivacaine will be concluded better than the other if found superior on opioid consumption.

24-48 hours: exparel will be concluded successful if found better than both placebo and bupivacaine in the 24-48 hours opioid consumption.

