## **F. Data Analysis**

Randomized groups will be compared for baseline balance using standard descriptive statistics and the standardized difference (difference in means or proportions divided by the pooled standard deviation).

**Primary Outcomes.** *Opioid consumption.* The following tests for superiority on opioid consumption will be conducted (see type I error control below): 1) 0-24 hours post-surgery: compare each of exparel and plain bupivacaine to placebo; and 2) 24-48 hours post-surgery: compare exparel to each of plain bupivacaine and placebo. Groups will be compared using linear regression on log-transformed morphine equivalents, with results reported as ratio of geometric means between each pair of interventions.

**Type I error control across Primary outcomes 1 and 2.** We will use a parallel gatekeeping procedure to control the type I error at 5% across the 2 primary outcomes. The 2 comparisons for the 0-24 hour period will constitute Set #1, and the 2 comparisons for the 24-48 hour period will constitute Set #2. Within each set we will use the Holm-Bonferroni (HB) multiple comparison procedure among the two comparisons. If either test in the first Set is significant (HB: significance criterion of 0.025 for smaller P-value and 0.05 for the larger), analysis will continue to Set #2. Otherwise, Set #2 will not be analyzed. If analysis proceeds to Set #2, the overall alpha for Set #2 will be  $0.05 \times$  proportion of significant tests in Set #1 (i.e., Set #2 alpha = either  $0.05 \times 1$  or  $0.05 \times .5 = 0.025$ ).

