### **Tertiary Outcomes.**

Groups will be compared on the collapsed composite of opioid-related side effects in the first 72 hours after surgery using chi-square tests. Groups will be compared on satisfaction with pain management at using a 0-10 point scale at 72 hours, or upon discharge if earlier, using the Kruskal-Wallis test overall and Wilcoxon rank sum test between interventions.

**Economic Analysis.** Finally, if a treatment effect between the 2 local anesthetic TAP blocks is detected, we will conduct a cost-effectiveness analysis estimating the incremental cost-effectiveness ratio (ICER) as the mean difference in costs divided by the mean difference in the primary outcome of time to return of sensation [or an analogous ratio using summaries which best fit the distribution of the data]. Total cost of hospital care and specific care costs will be estimated from data in the electronic medical records database. Data obtained from electronic medical records will include: operation time, surgery type, intraoperative opioid consumption, postoperative opioid consumption in PACU and in ward, breakthrough pain medication requirements, pain scores in PACU and ward, requirement of oxygen in PACU and ward, pruritus, requirement of antihistaminic medications, requirement of naloxone, itching, ambulation time, flatus, ileus, bowel movements (first time documented), constipation, length of stay and any side effects or complications.

**Interim Analyses.** We will use a group sequential design to conduct interim analyses at each 25% of the planned enrollment to assess efficacy and futility of the intervention using a gamma spending function. Specifically, we will maintain the overall alpha level (monitoring efficacy) at 0.05 using gamma parameter of -4 [similar to O'Brien Fleming], and power at 90% (monitoring beta, type II error) using gamma parameter of 0 [more aggressive, similar to Pocock]. Under the alternative hypothesis (assuming a true 50% relative reduction in the primary outcome) the cumulative probability of crossing an efficacy (and futility in parentheses) boundary at the 1st through 4th analyses will be 0.09 (0.025), 0.39 (0.05), 0.75 (0.075) and 0.90 (0.10) as shown in **Figure 1**.

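### The 0-24 h primary decision rules conflict: one requires a noninferiority finding that cannot be evaluated, another allows an active-versus-active claim outside the stated 5% control

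*Combined protocol and SAP*

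**What the plan says.** Three places in the combined protocol and SAP bear on the 0-24 h primary outcome.

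- **Section 2, Primary Aim 2 (success criteria).** One joint rule: both actives superior to placebo at 0-24 h, plus "noninferiority between plain bupivacaine and exparel groups in the first 24 hours of opioid consumption", plus liposomal bupivacaine (Exparel) superior to both other arms at 24-48 h.
- **Section 2, "Criterion for success of each intervention in each period".** Each active succeeds at 0-24 h if it beats placebo. Noninferiority is absent. A further conclusion is added: "As well, exparel or bupivacaine will be concluded better than the other if found superior on opioid consumption".
- **Section F, Data Analysis, Primary Outcomes.** "The following tests for superiority on opioid consumption will be conducted", and for the first period the list is "0-24 hours post-surgery: compare each of exparel and plain bupivacaine to placebo". On error control, "The 2 comparisons for the 0-24 hour period will constitute Set #1"; the two 24-48 h comparisons form Set #2. The gatekeeping covers these four tests. The analysis is linear regression on log morphine equivalents, and ratios of geometric means are to be reported for every pair of arms.

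The only threshold offered for opioid use is under the aims: "a difference of at least 10 mg in first 24 hours will be considered to be a clinically meaningful difference". The same 10 mg is repeated for 24-48 h. Section G sizes the trial for a ratio of 0.60 between any of the three arms in each period and does not mention noninferiority.

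**The concern.** The three places give different answers to the question of what counts as success at 0-24 h, and none is said to take precedence.

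First, a required part of the trial-level rule has no decision rule behind it. Whether it is met would have to be settled by a choice of margin and direction that the plan leaves open, in a trial that will "conduct interim analyses at each 25% of the planned enrollment".

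Second, a conclusion on primary outcome 1 is offered without a significance level and outside the procedure that is said to hold the error at 5% across both primary outcomes. If the trial draws that conclusion as the criteria permit, the 5% statement no longer describes everything being claimed.

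**Working it through.** **1. Side by side, 0-24 h**

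| Comparison | Primary Aim 2 rule | Per-intervention criteria | Section F tests |
|---|---|---|---|
| Each active vs placebo | superiority, both required | superiority, each alone | superiority, Set #1 |
| Exparel vs plain bupivacaine | noninferiority, required | superiority, either direction | no test listed |

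**2. Inputs (section G) and the plan's own figure.** CV 0.85, ratio 0.60, 90% power, 67 per group fixed and 79 per group maximum. Log-scale SD = sqrt(ln(1 + 0.85²)) = 0.7374; effect = −ln 0.60 = 0.5108. The per-comparison alpha is not stated. With n = 2(z₁₋α/₂ + z₀.₉₀)²·SD²/effect² (normal, then t):

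- α = 0.05: 44 / 45
- α = 0.025: 52 / 54
- α = 0.05/3: 57 / 58
- α = 0.05/6: 65 / 66, against the stated 67

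Scaling the t results at 0.05/6 by 3 × 79/67 gives 84 × 3 × 79/67 = 297 at CV 1.0 (stated 298) and 204 × 3 × 79/67 = 722 for a 25% reduction (stated 722). So the sizing looks as though six pairwise comparisons were allowed for (3 pairs × 2 periods), while section F tests four. This is an inference from the numbers.

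**3. Noninferiority.** SE = 0.7374·sqrt(2/n) = 0.1274 (n = 67) and 0.1173 (n = 79). With equal true means, one direction and one-sided 0.025, power = Φ(ln m/SE − 1.96). The margins m are illustrative.

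| Margin (ratio) | 67 per group | 79 per group |
|---|---|---|
| 1.10 | 11% | 13% |
| 1.20 | 30% | 34% |
| 1.25 | 42% | 48% |
| 1.50 | 89% | 93% |

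90% power needs m = exp((1.960 + 1.282)·SE) = 1.51 (67) or 1.46 (79). If both directions must be shown, power is 2Φ(ln m/SE − 1.96) − 1. That is about zero at 1.20 and 1.25, and 90% needs exp((1.960 + 1.645)·SE) = 1.58 (67) or 1.53 (79).

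Treating 10 mg as the margin does not settle it. As a ratio it is (mean + 10)/mean, and no mean is given: an assumed 20 mg gives 1.50, 50 mg gives 1.20 and 100 mg gives 1.10, which spans the whole table.

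**4. Active-versus-active superiority claim.** Simulation of section F's procedure: 1,000,000 trials per scenario, two-sided tests, no interim looks. Both actives have a true 0-24 h ratio of 0.60 to placebo and are equal to each other; there is no 24-48 h effect; between-period correlation runs from 0 to 0.7; 67 and 79 per group.

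| Tests run | Familywise error |
|---|---|
| Four listed tests | about 4.3-4.6% |
| plus the claim at 0.05/6 (inferred) | about 4.8-5.4% |
| plus the claim at 0.025 (assumed) | 6-7% |
| plus the claim at 0.05 (assumed) | 8-9% |

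**5. Testing the claim last.** Suppose it is tested at 0.05 only after all four listed tests succeed. If any of the four nulls is true, reaching the fifth test already required a false rejection, so no familywise error is added. If all four are false, the fifth test is the only possible error and is held at 0.05. In the equal-actives scenarios (late null, or Exparel effective late), simulation gives 3.6-4.6%.

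**The case against.** The best defence is that section F governs. It names its tests explicitly, the four can all be run, and the placebo and 24-48 h conclusions in the per-intervention criteria follow from them. On that reading the 0-24 h active-versus-active test is not run and no error is added. This stands as far as it goes, but the document does not say that section F takes precedence. If it does, the noninferiority clause and the sentence on one active being better have no test behind them and should come out.

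A second defence is that section G covers any pair of arms, and its sample size fits 0.05/6, at which the familywise error stays close to 5%. The fit is good, but sizing is not alpha allocation: section F assigns this comparison no level.

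Some stronger readings are tempting and are not supported:

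- **That the noninferiority clause inflates type I error.** It is joined to the other conditions by conjunction, so it can only make success harder. The gap is one of interpretability and power.
- **That the plan's error rate is 8-9%.** That needs an assumed 0.05 for a test whose level is not given.
- **That 10 mg is the margin.** It is described as a clinically meaningful difference, on an absolute scale that the ratio analysis does not use.
- **That the primary analysis as a whole cannot be evaluated.** Only the joint rule under Primary Aim 2 is affected.

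**Conclusion.** The conflict is real and is wrong as written. The joint success rule under Primary Aim 2 cannot be evaluated, because its noninferiority condition lacks a margin, direction, test and alpha. The 0-24 h conclusion that one active is better than the other lies outside the stated 5% control whatever level is used.

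How much error that adds depends on a level the plan does not give: nothing if section F's list governs, little at 0.05/6, and up to 8-9% in total at 0.05. These figures assume equal, effective actives early, no late effect and no interim looks. The noninferiority power figures assume equal true means and the section G variability, and the margins are illustrations.

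Separately, section F's own combination of Holm testing and alpha passing reaches about 6-7% when only one active works early. That is a different point. It adds no weight here and is not cured by the changes below.

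**What to change.** Before any interim analysis, state one primary success rule and make the two statements in section 2 and the test list in section F agree with it.

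- **Simplest.** Delete the noninferiority clause from the Primary Aim 2 criteria and the sentence on one active being better from the per-intervention criteria. Report the 0-24 h Exparel/plain bupivacaine ratio of geometric means with its 95% CI as descriptive; section F already plans ratios for every pair. Cost: wording only, and the formal 0-24 h claim between the actives is given up.
- **If the superiority claim is wanted.** Add it to section F as a fifth test at 0.05, run only after all four listed tests succeed. It takes no alpha or power from those four and needs no extra patients. Cost: the claim is available only when all four succeed.
- **If noninferiority is kept.** State a ratio-scale margin, the direction, the alpha and its place in the testing order, and disclose its power. This is not a wording change alone. At one-sided 0.025, one direction and 90% power, a margin of 1.25 needs 230 per group and 1.20 needs 344, against a maximum of 79. Any margin tighter than about 1.46 means accepting power below 90% or enrolling more patients.
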